8.1.1 Rationale for the trial population

Although previous trials with neridronic acid have been performed in subjects with CRPS-I, CRPS-I and CRPS Type II (CRPS-II) are likely to share the same pathophysiological basis (Oaklander and Horowitz 2015; Bruehl 2015).

There are no known methods to objectively distinguish between CRPS-I and CRPS-II subtypes, as electromyography and nerve conduction studies have low negative predictive value and do not rule out nerve abnormalities in CRPS-I. Furthermore, pathophysiological changes in bone, the principal target for efficacy of neridronic acid, may occur in patients diagnosed with CRPS-II.

Given the uncertain distinctions between these subtypes and lack of pathologic or pharmacologic basis for restricting treatment to CRPS-I, subjects with CRPS-II will also be included in this trial.

Reports from the literature suggest better responses to treatment when subjects are treated early after onset of the first symptoms (Wertli et al. 2014). There is no consensus on an exact time window for treatment. Preliminary data from an open-label trial employing a cumulative dose of neridronic acid 400 mg (KF7013-03), suggest clinically relevant decreases in pain intensity in a subgroup of subjects with a CRPS duration ≤ 2 years. The trial population in this trial will therefore be limited to this disease duration.

Subjects must be on stable therapy prescribed for CRPS for at least 1 month prior to randomization and allocation to maximize sensitivity to detect changes in pain intensity and other efficacy outcomes. Analgesic regimens including pro re nata (as needed) opioids or other analgesics are allowed if the regimen has been prescribed as part of a stable treatment. The investigator must select subjects who are anticipated to be able to maintain a stable treatment regimen for the first 12 weeks of the trial (up to and including Visit 8). Initiation of new therapies during the trial will be prohibited. Short courses of analgesics, including opioids (unless prohibited according to Section 1.4.2.1), will be allowed to be prescribed in the event of a severe pain flare.

8.1.2 Rationale for the investigational medicinal products and the selected doses

A previous pilot trial of neridronic acid, including cumulative intravenous doses of 200 mg, 300 mg, and 400 mg, suggested that doses below 400 mg were suboptimally effective (Varenna et al. 2004).

A previous randomized, double-blind, placebo-controlled trial performed by Abiogen Pharma S.p.A. demonstrated that a 400 mg cumulative intravenous dose of neridronic acid is effective, safe, and well tolerated in subjects with CRPS-I (Varenna et al. 2013; Clinical Study Report NERI-AS001-07). As the 4 x 100 mg dose regimen used in that trial has been approved for treatment of CRPS-I in Italy, the same dose regimen was selected for investigation in this trial.

In Italy, the recommended infusion time for 100 mg neridronic acid to treat osteogenesis imperfecta and CRPS-I is 2 hours. To limit the maximum concentrations (C_{max}) in this trial to levels similar to (and unlikely to exceed) those obtained in the KF7013-01 trial, in which 62.5 mg neridronic acid was infused in 2 hours, the infusion time has been extended to 4 hours.

8.1.3 Rationale for the number and the frequency of visits/assessments

The number and frequency of visits are considered to be sufficient to ensure subject safety and meet trial objectives.

8.1.4 Background and rationale regarding pharmacogenetic and omics testing

The European Medicines Agency (EMA; 2011) and United States FDA (2013) guidance documents recommend the conduct of pharmacogenetic assessments in clinical trials during drug development (Phase I to Phase III).

Genetic factors are suggested to play a role in CRPS (de Rooij et al. 2009). To further characterize protein-coding areas, signatures, and haplotypes related to CRPS-I, potentially relevant genes together with genes of the corresponding signaling pathways will be analyzed using genotyping of a panel of pre-selected single-nucleotide polymorphisms and proteomics of proteins encoded by these genes. The aim is to identify relevant pathways and gene-phenotype associations that will allow a phenotypic characterization of CRPS pain conditions. The associated single-nucleotide polymorphisms will be related to all corresponding proteins and then further analyzed using omics methods to identify potential biomarkers. In addition, the associated single-nucleotide polymorphisms will be used to identify potential genetic predispositions to CRPS and the function of these genes in response to treatment and disease progression, including potential linked side effects.

All measurements and analyses will be described in separate pharmacogenetic and omics plans.

8.2 Benefit/risk analysis

Potential benefits to subjects participating in this trial may include a reduction in pain and other symptoms of CRPS, as well as benefits of medical supervision from being in a clinical trial.

Risks to subjects participating in this trial are primarily related to the known side effects of neridronic acid and bisphosphonates as a class, particularly those associated with intravenous administration. Although doses of up to 400 mg of neridronic acid have been administered safely in

subjects with Paget's disease or CRPS-I, most of the clinical experience for neridronic acid has been at doses of 200 mg or below. In addition to drug-specific risks, there are also the risks of the procedures used in the trial.

In order to minimize the risk for the subject, it is obligatory that the investigator becomes familiar with all sections of the current neridronic acid investigator's brochure prior to the initiation of the trial and follows the warnings and directions thereof.

The trial population described in this protocol will consist of subjects with a diagnosis of CRPS, with onset of symptoms within the last 2 years, and who are medically stable and in stable follow-up therapy for CRPS for at least 1 month prior to allocation.

Subjects will continue to receive stable therapy for CRPS. Additional pain medication may be prescribed in the event of severe pain flare, with notification of the sponsor or sponsor's representative (i.e., medical monitor). Changes in analgesic medications and other treatments for CRPS may be permitted after Week 12, following notification of the sponsor or sponsor's representative (i.e., medical monitor). After Visit 10, investigators will assess the further need of concomitant treatment for CRPS, in particular opioids, and evaluate if the dose or frequency of these treatments can be decreased, or if treatment can be stopped completely. This will help to ensure that subjects in the trial will not suffer from untreated pain and that the subject's exposure to other analgesics will be decreased or stopped if they are no longer needed. Subjects may withdraw from the trial at any time, without giving a reason and without prejudice. However, subjects who withdraw will be asked to continue follow-up visits if at all possible for the scientific integrity of the trial as well as for their own safety.

Potential risks and risk management of neridronic acid

Acute phase reaction

The most common side effects associated with parenteral administration of aminobisphosphonates are flu-like symptoms, commonly referred to as "acute phase reaction" (Reid et al. 2010; Silverman et al. 2011). Symptoms include fever, myalgia, fatigue, headache, diarrhea, arthralgia, and bone pain. These are self-limiting and usually resolve after 24 hours to 48 hours. Symptoms of the acute phase reaction typically occur following the first administration and are absent or decreased following subsequent administrations. For symptomatic management of the acute phase reaction, oral acetaminophen (paracetamol) is recommended (for details, see Section 1.4.2). Non-steroidal anti-inflammatory drugs should not be used to alleviate the symptoms of the acute phase reaction due to their potential to cause acute changes in renal function, which may confound renal safety assessments.

Ocular effects

Eye disorders have been reported with neridronic acid and appear to be associated with the acute phase reaction. These events include anterior uveitis, episcleritis, conjunctivitis and ocular pain. As severe ocular inflammation may increase the potential risk of long-term vision loss, treatment with neridronic acid will be discontinued at first signs of ocular inflammation, followed by an ophthalmologic exam.

Hypocalcemia

Aminobisphosphonates are potent inhibitors of bone turnover, and are thus associated with a risk of hypocalcemia.

The normal compensatory mechanism is an increase in parathyroid hormone, which can trigger renal absorption of calcium and vitamin D3 production in response to a decreased calcium efflux from the skeleton after bisphosphonate therapy (Polyzos et al. 2011).

Subjects with abnormal blood calcium or magnesium concentrations, a history of disorders that impair the compensatory increase in parathyroid hormone, or concomitant use of any drug with known potential to cause hypocalcemia will be excluded from the trial. Retesting of out-of-range values is permitted once during the Enrollment Period. Albumin-corrected serum calcium should be considered when serum albumin is below the normal range (e.g., <3.5 g/dL).

All subjects will be provided with supplemental calcium and vitamin D, starting from Visit 1 and continuing through to the end of the trial (for details, see Section 1.4.2). Subjects with vitamin D levels below 30 ng/mL (75 nmol/L) will receive supplementation to achieve values of at least 30 ng/mL (75 nmol/L) prior to allocation to IMP. Subjects who do not reach vitamin D levels of at least 30 ng/mL (75 nmol/L) following appropriate supplementation will be excluded from the trial.

Renal toxicity

Based on the available data for neridronic acid, there is no clinical evidence for renal safety concerns to date. Nevertheless, renal toxicity was observed in non-clinical studies of neridronic acid and is regarded as a class effect of intravenous bisphosphonates. In most cases, signs for renal toxicity following administration of other intravenous bisphosphonates were transient and reversible after discontinuation of the drug or dose adjustment. Pronounced renal toxicity is a rare event, more common in long-term use, and there is a contributing role of pre-existing renal disease as well as other factors like other medication associated with renal toxicity and dehydration.

Bisphosphonates are rapidly cleared by the kidneys, potentially leading to a high concentration in kidney tissue during and immediately after the infusion. Dose and infusion time are the main factors related to renal toxicity.

In order to mitigate the risk of renal toxicity, subjects with evidence of severe renal impairment will be excluded (for details, see exclusion criterion 1).

Taking into account that renal toxicity due to intravenous bisphosphonates is related to the maximum drug concentration achieved and not the area under the curve of drug exposure (Khosla et al. 2012), 400 mg neridronic acid will be administered as 4 infusions of 100 mg neridronic acid administered over 240 minutes at Visit 2, Visit 3, Visit 4, and Visit 5 (and Visit 11, Visit 12, Visit 13, and Visit 14 during Treatment Period B) to subjects with no or mild renal impairment.

For subjects with moderate renal impairment, the dose will be adjusted (see Section 10.2).

Due to the potential for renal toxicity with neridronic acid as with other bisphosphonates, renal safety monitoring will be implemented in this trial together with defined stopping criteria (for details, see Section 9.3.2).

Cardiovascular

Despite the ability to transiently lower calcium levels, there has been no indication to date that bisphosphonates, as a class, cause prolongation of QT interval. Neridronic acid has not been studied in dedicated safety trials to evaluate a potential effect on the QT interval. Subjects with risk factors for QT prolongation or cardiac arrhythmia, including abnormal serum potassium levels, are excluded from this trial. Subjects will undergo regular 12-lead ECG examinations throughout the trial.

Medication-related osteonecrosis of the jaw

Osteonecrosis of the jaw is a rare adverse effect of bisphosphonate therapy, most commonly reported for patients with multiple myeloma and osteolytic bone metastases receiving repeated monthly infusions for treatment of skeletal related events and bone pain. Factors that may contribute to risk of osteonecrosis of the jaw include recent tooth extraction, unhealed or infected extraction sites, dental/periodontal disease, improperly fitting dentures causing injury, and prior radiation of the head or neck.

Invasive dental procedures should be avoided during the trial; however, subjects who require emergency dental surgery during the trial should proceed with appropriate treatment including prophylactic antibiotics and frequent follow-up. Subjects should be encouraged to use good dental hygiene (daily flossing and gentle brushing) throughout the trial.

Osteonecrosis of the external auditory canal

Osteonecrosis of the external auditory canal has been reported with bisphosphonates, mainly in association with long-term therapy. Possible risk factors for osteonecrosis of the external auditory canal include steroid use and chemotherapy and/or local risk factors such as infection or trauma. The possibility of osteonecrosis of the external auditory canal should be considered in patients receiving bisphosphonates who present with ear symptoms including chronic ear infections and/or local risk factors such as infection or trauma.

Atypical femoral fractures

Although a causal relationship has not been conclusively established, meta-analysis suggests there is an increased risk of atypical femoral fractures in long-term bisphosphonate users. These fractures have a low prevalence (1.1% of all femoral fractures), and the absolute risk to patients receiving bisphosphonates is low. Subjects should be advised to report any thigh, hip, or groin pain, and any patient who develops these symptoms should be evaluated for the presence of an incomplete femur fracture.

Other effects on bone

Although the potential for deleterious effects on bone following long-term treatment with bisphosphonates remains controversial to this day, no histomorphometric evidence of osteomalacia was reported at doses up to neridronic acid 250 mg in patients with Paget's disease of bone (McCloskey et al. 1987; Atkins et al. 1987), in contrast to findings following administration of the first generation bisphosphonate, etidronic acid.

Supporting the absence of any important effect on bone health, long-term neridronic acid treatment increased bone mineral density and lowered risk of clinical fracture in children and adults with

osteogenesis imperfecta. These results argue against a deleterious effect on bone mineralization due to neridronic acid.

However, the potential for deleterious effects of bisphosphonates on bone has been suggested in conditions of low bone turnover, such as renal osteodystrophy or other adynamic bone disease, although the benefit/risk profile in these conditions is unclear. In addition to exclusion of subjects with chronic kidney disease stage 4 and 5, subjects with known defects in bone mineralization or adynamic bone disease are excluded from the trial.

Pregnancy and breastfeeding

There are no adequate and well-controlled trials of neridronic acid in pregnant or lactating women. Although there are no data on fetal risk in humans, bisphosphonates do cause fetal harm in animals, and animal data suggest that uptake of bisphosphonates into fetal bone may be greater than into maternal bone. Therefore, neridronic acid should not be administered during pregnancy and lactation and as a result, pregnant or lactating women are excluded from participation in this trial.

Women of child-bearing potential must have a negative urine β -HCG pregnancy test at the Enrollment Visit and prior to each infusion of IMP. Trial subjects must use contraception as defined in inclusion criterion 6.

Risks related to acetaminophen and calcium and vitamin D supplementation

High doses of acetaminophen may cause hepatotoxicity and can lead to liver failure. Subjects who take acetaminophen for prevention or relief of symptoms of the acute phase reaction during the treatment periods will be reminded that the total dose must not exceed 4 g/day and that caution should be exercised since acetaminophen may be present in many over-the-counter drugs, particularly analgesic medications.

Recommended daily doses of calcium and vitamin D are lower than the tolerable upper intake level, at which there is no risk to healthy individuals (Ross et al. 2011; Rosen et al. 2012). Short courses of high doses of vitamin D are anticipated to pose no significant risk to trial participants.

General risks

Subjects will be regularly monitored for any changes in their medical status, e.g., vital signs, ECG parameters, and laboratory values, during the trial (see Section 12.1 for overall volume of blood samples).

Blood sampling may cause pain or bruise at the site where the blood is taken due to insertion of the needle. No other invasive procedure is planned. The total volume of blood to be collected and the planned sampling frequency do not pose any clear risk and are considered justifiable in the context of the trial and its duration.

Conclusion

As there are currently no FDA or EMA approvals for specific pharmacological treatments for CRPS, which is a severe pain condition with limited effective treatment options, the potential for benefit of neridronic acid is considered to outweigh the potential risk in this population. The need for controlled efficacy and safety trials of potential new treatments for CRPS justifies this trial on moral and ethical grounds.

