1.3.2 Exclusion criteria

Subjects will not be eligible for the trial if any of the following exclusion criteria apply. Subjects will only receive IMP if documentation is available showing that they do not meet any of these exclusion criteria.

1. Evidence of severe renal impairment (estimated glomerular filtration rate [eGFR] less than 30 mL/min/1.73 m² using the 2009 Chronic Kidney Disease Epidemiology Collaboration [CKD-EPI] creatinine equation [Levey et al. 2009] or a urinary albumin to creatinine ratio [ACR] greater than 150 mg/g), based on central safety laboratory data obtained prior to Visit 2. Note: a single repeat laboratory test is allowed.
2. Serum calcium or magnesium outside of the central laboratory's reference range, based on central safety laboratory data obtained prior to Visit 2 (2 repeat laboratory tests are allowed); a history of hypocalcemia or a metabolic disorder anticipated to increase risk for hypocalcemia (e.g., hypoparathyroidism); anticipated need for any new drug with known potential to cause hypocalcemia (e.g., aminoglycosides, new treatment with or dose adjustment of loop diuretics) during the trial.
Subjects on a stable dose of loop diuretics may receive treatment with IMP as long as no dosage increases in the diuretic medication are anticipated and calcium levels are in the reference range.
3. Vitamin D deficiency, defined as a 25(OH)D level less than 30 ng/mL (75 nmol/L), based on central safety laboratory data obtained prior to Visit 2 (up to 4 repeat laboratory tests are allowed). Subjects with vitamin D deficiency should receive appropriate supplementation during the Enrollment Period. A vitamin D level of at least 30 ng/mL (75 nmol/L) must be documented prior to allocation to IMP.

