4. Corrected QT interval (according to Fridericia's formula; QTcF) greater than 470 ms (average of 3 ECGs obtained at Visit 1) according to central ECG reading facility evaluation or QTcF greater than 470 ms at pre-dose ECG at Visit 2 according to the investigator's judgment; serum potassium outside the central laboratory's reference range at Visit 1 (a single repeat laboratory test is allowed); clinically unstable cardiac disease, including: unstable atrial fibrillation, symptomatic bradycardia, unstable congestive heart failure, active myocardial ischemia, or an indwelling pacemaker; evidence of complete left bundle branch block; complete atrioventricular block; history of Long QT Syndrome or a relative with this condition; or any history of or other known risk factor for torsade de pointes.

-
5. Subjects receiving medications with a known risk of torsades de pointes within 7 days prior to allocation. Subjects receiving selective serotonin re-uptake inhibitor antidepressants (e.g., citalopram, escitalopram) are eligible if the QT interval values do not meet the exclusion criteria, the medication was started at least 1 month prior to Visit 1, the dose is stable, and the dose is anticipated to remain stable throughout the trial.
 6. Any prior use of a bisphosphonate for treatment of CRPS, any prior administration of a bisphosphonate within the previous year, anticipated requirement for treatment with a bisphosphonate for another condition such as osteoporosis during the trial, or administration of denosumab (Prolia[®]) or other bone turnover suppressing drugs within 6 months prior to Visit 1.
 7. History of any allergic or hypersensitivity reaction to neridronic acid or other bisphosphonate, acetaminophen, or to vitamin D or calcium supplements.
 8. Recent tooth extraction or other invasive dental procedure (within 3 months prior to Visit 1), unhealed or infected extraction site, or significant dental/periodontal disease (e.g., impacted molars, severe tooth decay, foci of infection) that may pre-dispose to need for tooth extraction or other invasive dental procedures during the trial. Subjects with indeterminate, suspicious or unreliable dental history, in the opinion of the investigator, must undergo a dental examination prior to receiving treatment.
 9. Evidence of denture-related gum trauma or improperly fitting dentures causing injury.
 10. Prior radiation therapy of the head or neck (within 1 year of Visit 1).

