 11. History of malignancy within 2 years prior to Visit 1, with the exception of basal cell carcinoma.
 12. Use of nerve blocks, ketamine infusions, intravenous immunoglobulin, acupuncture, electromagnetic field treatment, or initiation/implementation of radiofrequency ablation or other sympathectomy procedures, or peripheral nerve stimulation within 6 weeks prior to Visit 1.
 13. Evidence of current alcohol or drug abuse, or history of alcohol or drug abuse within 2 years of Visit 1, based on subject history and physical examination and according to the investigator's judgment.
 14. Any other severe medical condition, including severe depression, or any other severe mood disorder, that in the opinion of the investigator may affect efficacy or safety assessments or may compromise the subject's safety during trial participation.
 15. Women who are pregnant or breastfeeding.
 16. Elevated aspartate aminotransferase or alanine aminotransferase greater than 2-fold upper limit of normal, based on central safety laboratory data obtained at Visit 1, or current evidence of chronic liver disease. Safety laboratory testing may be repeated prior to Visit 2, and subjects will be allowed in the trial if results of 2 consecutive tests, at least 3 days apart, are less than or equal to 2-fold upper limit of normal.
 17. Participation in another investigational drug trial within 3 months prior to Visit 1, or any previous trial involving neridronic acid.
 18. Subject is engaged in litigation related to their disability from CRPS in which monetary gain or loss (or other compensation) may affect their objective participation in the trial.
 19. Subjects taking forbidden concomitant medications/therapies or not being able to follow the rules of use of concomitant treatment (see Section 1.4.2).

20. Subjects incapable of giving informed consent.

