9.2 Inclusion/exclusion criteria

The trial population must comply with the inclusion/exclusion criteria given in Section 1.3.

Subjects will only receive IMP if documentation is available showing that they comply with all of these criteria.

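### Section 8.2 says subjects with known bone mineralization defects or adynamic bone disease are excluded, but no eligibility criterion in Section 1.3 contains that exclusion

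*Protocol*

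**What the plan says.** Section 8.2, under other effects on bone, raises the possibility that bisphosphonates harm bone when turnover is low. It gives renal osteodystrophy and adynamic bone disease as examples and calls the benefit/risk profile in such conditions unclear. It then says that, besides subjects with chronic kidney disease stage 4 and 5, "subjects with known defects in bone mineralization or adynamic bone disease are excluded from the trial".

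Eligibility is fixed elsewhere. Section 9.2 says: "The trial population must comply with the inclusion/exclusion criteria given in Section 1.3". Section 1.3.2 opens with "Subjects will not be eligible for the trial if any of the following exclusion criteria apply" and lists criteria 1 to 20. Section 10.3 allocates subjects who satisfy all inclusion criteria and meet no exclusion criterion. Section 1.3.3 gives a separate list for entry to Treatment Period B.

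The only general clause in Section 1.3.2 is criterion 14. It begins "Any other severe medical condition, including severe depression, or any other severe mood disorder, that in the opinion of the investigator" and goes on to require that the condition may affect the assessments or the subject's safety.

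**The concern.** Section 8.2 states the exclusion as a fact about the trial. A reader of that section, including an ethics committee, would take it that a subject with a known mineralization defect or adynamic bone disease cannot enter. A site that applies Section 1.3 as written has no item under which to check or document that these conditions are absent, so it could admit a subject whom the protocol elsewhere describes as excluded. What is at stake is the safety of those subjects and the accuracy of the risk description.

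**Working it through.** No arithmetic applies. The check sets the sentence in Section 8.2 against every list that could put it into effect.

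**Step 1: the governing list.** Sections 9.2 and 10.3 both tie entry and allocation to the criteria in Section 1.3. Section 8.2 adds no criterion of its own.

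**Step 2: Section 1.3.2.** The numbering runs from 1 to 20 without a gap, so redaction or text extraction does not explain a missing item. The criteria nearest to the point are:

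| Criterion | What it tests | Reach for the conditions in Section 8.2 |
|---|---|---|
| 1 | eGFR below 30 mL/min/1.73 m², or urinary albumin to creatinine ratio above 150 mg/g | Implements the stage 4 and 5 half of the sentence. Section 1.4.1 defines stage 3b as eGFR 30 to below 45, so stages 4 and 5 lie below 30. |
| 2 | Calcium or magnesium out of range, history of hypocalcemia, or a metabolic disorder expected to raise hypocalcemia risk | Incidental. Aimed at hypocalcemia and does not name bone disease. |
| 3 | 25(OH)D below 30 ng/mL before allocation | Incidental. A laboratory threshold that may be corrected by supplementation during enrollment. |
| 6 | Past, recent or anticipated use of bisphosphonates or other bone turnover suppressing drugs | Incidental. Excludes by drug use and not by diagnosis. |
| 14 | A severe condition that the investigator considers relevant to safety or assessments | Discretionary. Needs both severity and the investigator's opinion. |

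The other 15 criteria concern unrelated matters, such as cardiac, dental, liver, pregnancy, prior-trial, litigation and consent issues. Count: 0 of 20 name a bone mineralization defect or adynamic bone disease.

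**Step 3: Section 1.3.3.** The Treatment Period B list repeats the renal, calcium and magnesium, vitamin D, QT, dental, liver and forbidden-medication items. It names neither condition. It also repeats neither the metabolic-disorder clause of criterion 2 nor the general clause of criterion 14, although it does require that no other criterion for trial or IMP discontinuation is met.

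**Step 4: other places.** The seven inclusion criteria in Section 1.3.1, the forbidden medications in Section 1.4.2.1 and the discontinuation reasons in Table 2 of Section 9.3.2 contain no such item. The changes to Sections 1.3.2 and 1.3.3 that Amendment 01 records neither add nor remove one.

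**Step 5: who is left.** Take a subject with one of these conditions on record who:

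- has the disease judged non-severe;
- has calcium, magnesium and vitamin D within the required limits;
- has eGFR of at least 30 and an albumin to creatinine ratio of at most 150 mg/g;
- has no history of hypocalcemia and no disorder expected to raise its risk;
- has no relevant drug use.

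This subject meets none of the 20 exclusions on account of the bone disease, yet falls under the sentence in Section 8.2. The two texts give different answers for the same person.

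**The case against.** The strongest reply is that much of this group is already kept out. Criterion 1 removes stage 4 and 5 kidney disease, which bears on the renal osteodystrophy that Section 8.2 mentions. Criteria 2, 3 and 6 remove many subjects with disturbed mineral metabolism or bone-active treatment. Principal investigators also sign their agreement to the whole protocol, so one who has read Section 8.2 may use criterion 14, and Section 9.3.2 allows permanent discontinuation of IMP for undue risk. All of this stands and narrows the uncovered group. A reader might infer that anyone with a mineralization defect passes unless the investigator calls it severe; the documents do not support that, because criteria 1, 2, 3 and 6 can also apply. The remaining cover is nevertheless incidental or discretionary, whereas Section 8.2 describes a flat exclusion of known disease.

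A reader might also infer that the overall benefit/risk conclusion rests on a safeguard that the trial does not apply. That goes too far. The conclusion of Section 8.2 argues from the lack of approved treatments, the limited options and the need for controlled trials, and does not mention bone disease. The bone paragraphs argue first from clinical evidence: no osteomalacia at doses up to 250 mg in Paget's disease, and better bone density with fewer fractures in osteogenesis imperfecta. The exclusion is one added mitigation there.

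**Conclusion.** The inconsistency is real. Section 8.2 states a categorical exclusion, and the lists that decide entry and re-treatment do not contain it. Criteria 1, 2, 3, 6 and 14 give partial cover, so it would be wrong to say that no protection exists; the accurate statement is that the mitigation is not in force as a categorical exclusion.

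The documents give no prevalence from which to count affected subjects, and the number is probably small. The sample size, power, type I error and primary analysis do not depend on it. The weight of the point lies in subject safety and in a correct risk statement. It assumes only that sites apply Section 1.3 as written, as Sections 9.2 and 10.3 direct.

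There is a second sign that Section 8.2 has drifted from Section 1.3: it allows one retest of out-of-range calcium or magnesium during enrollment, whereas criterion 2 allows two.

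**What to change.** Reconcile Section 8.2 with Sections 1.3.2 and 1.3.3 so that the stated exclusion and the operative criteria say the same thing for both first treatment and re-treatment. The sponsor may do this by changing the criteria or by correcting the sentence; the clinical rule is the sponsor's to set. The calcium and magnesium retest allowance can be aligned in the same pass.

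The cost is a short wording change in the next amendment. If the sponsor changes the criteria, sites would also have to document the item. Section 12.2.3 already collects medical history for the previous 3 years and older history considered relevant. That probably captures known disease, but the section does not require medical records to be obtained, so the sponsor should confirm that the history is sufficient.
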